**Safety and Monitoring:**

1. **Comfort:** Subjects will be asked to verbally rate (1-5 scale) severity, location and quality (self described) of any discomfort immediately prior to the scan, after each block during the scans, immediately after the stimulation session and at 10 minutes after the stimulation sessions. If any discomfort persists at 10 minutes after stimulation, treatment and ongoing assessment will be arranged as needed by the study physician.

2. **Cognitive Effects:** Baseline memory, attention and verbal reasoning will be assessed using the Digits span test from the WASI, which assesses short-term memory and attention. This will be repeated 10 minutes after the stimulation. Subjects will also be asked open ended questions about any changes in their thinking or cognitive status. Research staff will follow up with participants in the second and third sessions and 5 to 14 days after the third session to query the persistence or emergence of any cognitive changes.

3. **Psychiatric Effects:** Emotional, motivational and behavioral symptoms will be assessed using the PANAS (Positive and Negative Affect Scale) before stimulation and immediately following stimulation.

**Phase 3. Neural effects on behavior.** In Phase 3, we will test the effectiveness of Temporal Interference-NDBS on reducing smoking and cigarette craving in heavy smokers. To test this, we will proceed with two stages. In the first stage (pilot), we will recruit heavy smokers into three groups, then ask them to abstain from smoking. One group will receive TI-NDBS to the left and

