right insula. Another group will receive TI-NDBS over the nucleus accumbens. Another group will receive TI-NDBS to the anterior cingulate cortex. We will not target these brain areas in any particular order. Prior to stimulation, subjects will be administered a questionnaire to assess their physical experiences and sensations using a 5-point Likert-scale. Subjects will also be given the Nicotine Dependence Syndrome Scale to assess baseline Nicotine Dependence. In addition, we will measure total real-time ad lib nicotine vapor inhalation during a 60 minute stimulation session. At the start of the stimulation, the current will increase slowly at a constant rate for 30 seconds until it reaches the appropriate intensity. At the end of the stimulation, the current will decrease slowly for 30 seconds until it reaches zero. Every ten minutes, we will ask subjects to self-report their level of craving on a Likert scale of 1-10. We will identify whether TI-NDBS to the insula or nucleus accumbens or cingulate is more effective stimulation at decreasing cravings. In the second stage of Phase 3, we will take the two most promising of the three brain regions and repeat the procedure of stage 1, but with a larger sample size. The third group will receive sham stimulation as a control. In both stages, immediately after stimulation, subjects will complete the stimulation experience scale and then again 30 minutes later. We will then follow up with subjects every day, up to three times per day, for a period of 1 week afterward using Ecological Momentary Assessment (EMA) via a smartphone app (LifeData) to monitor cigarette and/or vaping use and craving. The questions that will be used in the app are in a script attached (see EMA follow up questions). In Phases 1, 2, and 4 subjects are paid \$25/hr. In Phase 3, subjects are paid \$40/hr. In addition, in Phases 3 and 4, subjects are paid \$5/day for providing ecological momentary assessment data outside of the lab sessions, and \$10 bonus for completing 7 consecutive days of ecological momentary assessment (EMA). Payment will be made at the end of each day's lab session in cash, and for phase 3, by check after the EMA period ends.

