conventional transcranial direct current stimulation for smoking reduction. To test this, we will recruit another group of subjects who are heavy smokers into three groups, then ask them to abstain from smoking. Prior to stimulation, subjects will be given the NDSS to determine baseline nicotine dependence. The first group will receive standard transcranial direct current anodal stimulation of the right DLPFC and cathodal stimulation of the left DLPFC (F3 and F4 in the 10/20 system). The second group will receive TI-NDBS to either the nucleus accumbens or anterior insula or anterior cingulate, depending on which is found to be more effective in Phase 3. The third condition will be sham. The strength of the stimulation and duration will be the same as in previous phases. Prior to stimulation, subjects will be administered a questionnaire to assess their physical experiences and sensations using a 5-point Likert-Scale. Immediately after stimulation, subjects will complete the stimulation experience scale, then complete the scale again 30 minutes later. In addition, we will assess craving levels every 10 minutes during the stimulation period. We will repeat this for five consecutive days. We will then follow up with subjects every day, up to three times per day, for 1 week after starting the tDCS, using EMA via a free smartphone app (ilumivu.com) to monitor cigarette use and craving. The questions that will be used in the app are in a script attached (see EMA follow up questions). We will compare the sham vs. tDCS vs. TI-NDBS groups to identify differences in craving and relapse. We expect to find that TI-NDBS leads to reduced craving and drug use relative to sham or tDCS. The procedure in this phase will not add anything new, except testing subjects with tDCS in addition to TI-NDBS and sham.

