## **6.0 Statistical Analysis and Sample Size:**

In phase 1, we will assess tolerability with an initial cohort of 3 stimulation subjects. Our aim here is to identify any potential adverse effects, using two approaches. We will monitor the stimulation condition for clinically significant adverse effects such as seizures, prohibitive pain, etc, though we do not expect this based on all the literature from earlier studies.

In phase 2, we will conduct a pilot assessment to determine whether and how the stimulation immediately influences neural activity. As this is a within-subjects pilot design intended to estimate the effect size of neural activation, we will scan 10 subjects, comparing the neural activation in each subject during the stimulation period with neural activation in the same subject during the no-stimulation periods. We do not have a power analysis for this phase yet, because the whole point is to perform a pilot study in order to estimate the effect sizes. We anticipate that 10 subjects will be sufficient to estimate the effect sizes.

In phase 3, we will proceed in two parts. During the first pilot part, we will recruit 5 subjects in each of 3 groups, to identify which two of the three candidate brain regions seem most promising sites of stimulation to reduce nicotine craving and consumption. Once we identify the two more promising sites of stimulation, we will proceed to the second part. We do not have a power analysis for this part because again, we are looking to estimate the relative effect sizes for one stimulation site compared to another. For the second part, we will recruit 45 subjects who are heavy smokers into three groups of 15 each, then ask them to abstain from smoking for several hours prior to the session. The first group will receive TI-NDBS over the most promising site. The second group will receive TI-NDBS over the second most promising site. The third group will receive sham stimulation. We will measure total real-time ad lib nicotine vapor inhalation during a 60 minute stimulation session, and every ten minutes, we will ask subjects to

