self report their level of craving on a Likert scale of 0-10. We will identify whether TI-NDBS over the insula or nucleus accumbens is more effective than sham stimulation. We will then follow up with subjects 1 week afterward, using ecological momentary assessment (EMA) via smartphone apps (ilumivu.com) to assess cigarette use and craving. We expect to find that TI- NDBS reduces craving and cigarette consumption relative to sham. **Analysis and predictions:** We predict that TI-NDBS will outperform tDCS at reducing smoking and cigarette craving, which in turn will outperform sham stimulation. We will sum the total inhaled nicotine vapor over the 60 minute session and perform pairwise t-tests to determine if total drug intake is lower with one of the stimulation groups vs. sham. Also, we will average the self reported craving levels across each subject during the 60 minute session, and we will perform pairwise tests to determine if stimulation lowers self reported craving. During the 7 days following the stimulation session, we will give subjects the ilumivu app on their smartphones (or a loaner phone if needed), and we will notify them daily to request a self report of their level of craving and cigarette use in the preceding 24 hours. We will average these measures for each subject and perform an omnibus ANOVA (time point by group), followed by post-hoc pairwise tests to determine whether the stimulation led to longer lasting effects relative to sham. We will perform post-hoc tests for each of the 7 days to identify any differences in the duration of stimulation effects. For a power analysis, we do not yet know how many subjects will be necessary to achieve statistical power in the second part of phase 3, because we do not yet know what the effect sizes are. Nevertheless we anticipate that 15 subjects per group will provide a solid estimate of the effect sizes of stimulation relative to sham, so that we can write a grant to scale up the number of subjects based on a power analysis.

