In phase 4, we will compare TI-NDBS vs. conventional transcranial direct current stimulation for smoking reduction. To test this, we will recruit another 45 subjects who are heavy smokers into three groups of 15 each, then ask them to abstain from smoking. The first group will receive standard transcranial direct current anodal stimulation of the right DLPFC and cathodal stimulation of the left DLPFC (F3 and F4 in the 10/20 system). The second group will receive TI-NDBS to the most promising site as determined in phase 3. The third condition will be sham. We will assess craving levels every 10 minutes during the 60 minute stimulation period. We will repeat this for five consecutive days. We will then follow up with subjects 1 week after starting the tDCS, using ecological momentary assessment (EMA) via smartphone apps (ilumivu.com) to monitor cigarette use and craving. We will compare the sham vs. tDCS vs. TI-NDBS groups to identify differences in craving and relapse. **Analysis and predictions:** We expect to find that TI-NDBS leads to reduced craving and drug use relative to sham or tDCS. We will carry out the same statistical tests as in Study 1. As before, we do not yet know the effect sizes but will aim to estimate them based on the initial 45 subjects.

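### Phases 3 and 4 state no random or concealed allocation to arms, and the between-arm tests ignore the baseline NDSS collected from every smoker

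*Combined protocol and SAP*

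**What the plan says.** **Arms.** The Phase 3 description in section 3.0 says "we will recruit heavy smokers into three groups, then ask them to abstain from smoking". Section 6.0 gives the sizes. In the pilot part of Phase 3, "we will recruit 5 subjects in each of 3 groups"; in the second part, "we will recruit 45 subjects who are heavy smokers into three groups of 15 each". Phase 4 recruits another 45 smokers in the same layout.

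**Allocation.** None of these places says how a subject is assigned. For this study, randomisation is named only in the opening checklist of topics a protocol should cover. Section 3.0 says the three target sites will be taken in no set order, and the Recruitment section fills session slots by availability. Neither is an allocation method. The TI device section describes a single-blind design in which the experimenter learns the current delivered.

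**Baseline dependence.** For Phase 3, "Subjects will also be given the Nicotine Dependence Syndrome Scale to assess baseline Nicotine Dependence". For Phase 4, "Prior to stimulation, subjects will be given the NDSS to determine baseline nicotine dependence".

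**Analysis.** For total intake, section 6.0 will "perform pairwise t-tests to determine if total drug intake is lower with one of the stimulation groups vs. sham". Session craving, averaged per subject, also goes to pairwise tests. For the EMA outcomes the plan will "perform an omnibus ANOVA (time point by group), followed by post-hoc pairwise tests". For Phase 4, "We will carry out the same statistical tests as in Study 1"; the term Study 1 is not defined, and I read it as Phase 3. No covariate is named for any of these analyses.

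**The concern.** There are two linked gaps.

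The first is allocation. A t-test's 5% error rate allows for chance imbalance between arms when assignment is random. If the arm can depend on time slot, calendar period or staff choice, that guarantee is lost, and nothing stated rules these out. This does not show that bias will occur; it shows that the plan does not prevent it.

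The second is efficiency. How dependent a smoker is may well predict how much that smoker inhales and craves. With 15 per arm, leaving out a baseline value already in hand gives up precision in proportion to that correlation.

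The Phase 3 results choose the site carried into Phase 4, and section 6.0 wants effect sizes from these samples to power a later grant. Bias or avoidable noise would pass into both.

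**Working it through.** The plan gives no power, alpha, SD or target effect for these comparisons, so there is no figure of its own to reproduce.

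**Inputs**
- From section 6.0: n = 15 per arm, or 5 in the Phase 3 pilot part; three arms.
- From section 3.0: d = 0.71, a literature figure for cigarette consumption after 5 days of tDCS. It is a benchmark only, because the plan says it cannot yet estimate a TI-NDBS effect.
- Assumed: two-sided 0.05, SD 1, no dropout, equal variances, and r (the NDSS-outcome correlation) from 0 to 0.7. The entry rule of at least 3/4 pack per day may narrow the range of dependence and so lower r.

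**Step 1. Planned two-arm t-test.** Variance of the difference = 2/15, SE = 0.365, 28 df. The noncentrality is 0.71/0.365 = 1.94, so power is 46.7%. The 95% half-width is 2.048 × 0.365 = 0.75 SD.

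**Step 2. Adjustment for NDSS.** The variance becomes (1 − r²) × (2/15) × k, where k allows for chance covariate imbalance.
- Two arms: k = 1 + 1/26, 27 df.
- One model for all three arms: k = 1 + 1/40, 41 df. Its unadjusted counterpart has 42 df and 47.6% power.

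| r | Two-arm power | Two-arm half-width (SD) | Three-arm power |
|---|---|---|---|
| Unadjusted | 46.7% | 0.75 | 47.6% |
| 0 | 45.2% | 0.76 | 46.6% |
| 0.2 | 46.7% | 0.75 | 48.2% |
| 0.3 | 48.8% | 0.73 | 50.2% |
| 0.5 | 56.5% | 0.66 | 58.1% |
| 0.7 | 73.1% | 0.55 | 74.7% |

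A simulation of 40,000 trials per value of r gave 45.4, 46.9, 48.9, 56.7 and 73.2% for the two-arm column. Adjustment breaks even at r of about 0.20 in the two-arm fit and about 0.16 in the three-arm fit.

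**Step 3. Chance imbalance under true randomisation.** P(|gap| > 0.5 SD) = 2 × [1 − Φ(0.5/√(2/n))].
- n = 15: 0.5/0.365 = 1.37, probability 17%.
- n = 5: 0.5/0.632 = 0.79, probability 43%.

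**Step 4. A systematic gap.** Suppose a non-random rule produced a 0.5 SD gap in NDSS (assumed). The unadjusted contrast shifts by 0.5 × r, which is 0.15, 0.25 or 0.35 SD at r = 0.3, 0.5 or 0.7. Dividing by 0.365 gives noncentralities of 0.41, 0.68 and 0.96. The nominal 5% t-test (28 df) would then reject a true null about 7, 10 or 15% of the time.

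**The case against.** **Adjustment is a choice, not a correction.** An unadjusted t-test between randomised arms is valid, and the plan never promises an NDSS-adjusted analysis. This stands. The gain is negligible at r of 0.3 or below, and r is unknown.

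**The benchmark is borrowed.** The 0.71 figure belongs to another stimulation method and another outcome. The plan presents these samples as estimating effects rather than testing them, and Phase 4 repeats sessions over five days, which a single-measure calculation does not describe. This stands as a limit on the power column. The half-widths do not use d, and they are the relevant measure for an estimation aim.

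**The 17% and 43% are not evidence of a defect.** They arise under fair randomisation, and the t-test already allows for them. This is correct: they show how easily small arms differ. The 0.5 SD systematic gap is assumed, and the plan implies neither its size nor its direction.

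**Adjustment cannot replace randomisation.** Unmeasured differences would remain. This is also correct, and it makes allocation the more serious half.

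**Details.** The Recruitment section gives the dependence scale a slightly different name, and the plan does not say which score would be used. Some pages were removed before review, so absence can be claimed only for the text seen. Neither point supplies an allocation method or a use for the NDSS.

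**Conclusion.** The concern holds on both counts, and the plan should be changed.

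The allocation gap is a matter of text and depends on no assumed correlation: no random or concealed method is stated for either part of Phase 3 or for Phase 4. Its numerical effect cannot be known in advance; the shifts of 0.15 to 0.35 SD rest on an assumed 0.5 SD gap in NDSS.

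The adjustment gap is a loss of precision whose size depends on r. In the recommended three-arm model, the change in power runs from a loss of about 1 point at r = 0 to a gain of about 27 points at r = 0.7 (47.6% to 74.7%), with d = 0.71 as a benchmark. Confidence is medium, because the documents do not give r.

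**What to change.** 1. **Allocation.** Assign subjects in both parts of Phase 3 and in Phase 4 from concealed, computer-generated permuted-block lists, one per part, with no stratification in the 5-per-arm part. Mix block sizes of 3 and 6, because an experimenter who knows the condition could predict fixed blocks. A single random permutation of the whole list would also give exact balance. Someone who does not enrol subjects should hold the list and release each assignment only after the NDSS is complete.

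2. **Analysis.** For the 15-per-arm comparisons, replace the pairwise t-tests with one linear model containing arm and baseline NDSS, for total intake and for mean craving. Report each arm contrast with its 95% CI. Add baseline NDSS to the EMA time-by-group model. Name the scale consistently and state which score enters. If breath CO is ever used as a covariate, use only a value taken before the first stimulation.

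**Cost.** SAP wording and three short lists, with no new measurement, visit or subject. The model spends one degree of freedom. Against an unadjusted three-arm fit it loses about 1 point of power if r is 0; against the planned two-arm t-test it loses essentially nothing (46.7% to 46.6%). Both changes should be made before enrolment: allocation cannot be repaired afterwards, and a covariate chosen after seeing the data carries less weight.

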electrode placement. The software simulates the electrical fields generated given a set of electrode locations in the 10/20 coordinate system. With this, we are able to specify a target brain region, then run a software optimization routine that determines the optimal electrode placement to target the desired brain region. After some *in silico* testing, we found that the electrode placement can be determined in the standard 10/20 coordinate system using a standard brain image template (the Montreal Neurological Institute or MNI template.) Furthermore, once the electrode locations are calculated, they can be applied to all subjects without subject-specific structural MR images, because the between-subject variation in 10/20 coordinates vs brain regions is small relative to the extent of the temporal interference region. Put another way, the marginal increased accuracy due to optimization on a subject-specific structural MR image vs. an MNI template brain is negligible. This will allow us to determine the electrode placements with high accuracy, so that we can specifically target the desired brain regions.

**Phase 1. Tolerability.** In phase I, we will test the safety of the temporal interference non-invasive deep brain stimulation (TI-NDBS) device on non-smokers (n=3). Subjects will be administered a questionnaire to assess their physical experiences and sensations using a 5-point Likert-scale (Stimulation experience scale attached in Notes & Attachments and is the same scale used in all four stages of the protocol). After baseline measures, subjects will be sitting in a chair and have the electrodes (measuring approximately 2 cm by 2 cm) attached to the scalp.

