#### **Safety and Monitoring:**

- 1. Comfort:** Subjects will be asked to rate (1-5 scale) severity, location and quality (self described) of any discomfort using the attached stimulation experience scale immediately prior to the stimulation, immediately after each 10 minute stimulation block, and at 10 minutes after the stimulation session. If any discomfort persists at 10 minutes after stimulation, treatment and ongoing assessment will be arranged as needed by the study physician.
- 2. Cognitive Effects:** Baseline memory, attention and verbal reasoning will be assessed using the Digits span test from the WASI, which assesses short-term memory and attention. This will be repeated 10 minutes after the stimulation. Subjects will also be asked open ended questions about any changes in their thinking or cognitive status.
- 3. Psychiatric Effects:** Emotional, motivational and behavioral symptoms will be assessed using the PANAS (Positive and Negative Affect Scale) before stimulation and immediately following stimulation.
- 4. COVID-19 safety:** Subject and experimenter, both wearing masks, enter the testing room. Experimenter places electrodes on subject's head and adjusts them. Experimenter gives the subject an e-cigarette mouthpiece and an exhaust device to exhale into (which has a carbon and HEPA filter to filter the subject's exhaled breath and nicotine vapor), with instructions for the subject to remove their facemask after the experimenter has left the room, inhale from the e-cigarette per protocol, and exhale into the exhaust device. Experimenter leaves the room, after which subject removes their own facemask. Subject proceeds to do the experiment and puts their facemask back on before the experimenter again enters the room.

**Phase 4. Relative effectiveness of stimulation.** In phase 4, we will compare TI-NDBS vs.

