For tDCS to the dorsolateral prefrontal cortex, we will place electrodes over F3 and F4. For TI-NDBS, we will use finite element methods ([simnibs.org](http://simnibs.org) or [sim4life](http://sim4life)) to determine where to place each of four electrodes (two pairs) in order to target the desired brain region. Each smoking subject will be allowed *ad lib* intake from our custom e-cigarette, which measures total inhaled vapor and thus nicotine intake (as we verified in Velez et al., 2015). As a measure of short-term neurostimulation effectiveness, we will compare total nicotine inhaled during stimulation for tDCS, TI-NDBS, and sham subjects. We will also ask for periodic self reports of craving during stimulation, i.e. “How much do you want to smoke?”, on a Likert scale of 0-10. We will compare self-reported craving across different stimulation conditions. For long-term assessment, we will use ecological momentary assessment, with the [Illumivu.com](http://Illumivu.com) system. Subjects will be prompted 3 times a day (morning, afternoon, and evening) between neurostimulation sessions and for the next two weeks following neurostimulation to report how many cigarettes they smoked in the preceding time period, and how much they are craving cigarettes at the moment. We will use this information to assess how strong the effect of stimulation is even after the stimulation session has ended. In the lab, we will measure recent smoking by measuring breath carbon monoxide (CO, Smokerlyzer PiCO).

[figure not shown]

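### Cheap precision gain, mainly for the second part of Phase 3: schedule one craving rating before stimulation and use it as a covariate

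*Combined protocol and SAP*

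**What the plan says.** The craving analysis is in section 6.0, Phase 3: "we will average the self reported craving levels across each subject during the 60 minute session, and we will perform pairwise tests". It names neither a covariate nor a change from baseline. For Phase 4, section 6.0 reuses the same tests.

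The craving ratings are timed as follows.
- 3.0 Design, Phase 3: "Every ten minutes, we will ask subjects to self-report their level of craving on a Likert scale of 1-10". Section 6.0 gives the same interval but a range of 0-10.
- New technology: "We will also ask for periodic self reports of craving during stimulation", also on 0-10.
- 3.0 Design, Phase 4: "we will assess craving levels every 10 minutes during the stimulation period".

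The measures expressly placed before stimulation are these.
- A questionnaire on physical sensations (Phases 3 and 4).
- Dependence. Phase 3: "Subjects will also be given the Nicotine Dependence Syndrome Scale to assess baseline Nicotine Dependence". Phase 4: "Prior to stimulation, subjects will be given the NDSS to determine baseline nicotine dependence".
- Discomfort and digit span (Safety and Monitoring).
- Affect: "Emotional, motivational and behavioral symptoms will be assessed using the PANAS (Positive and Negative Affect Scale) before stimulation and immediately following stimulation".

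None of these is described as a rating of current craving. Two places leave some doubt. The TI device section lists nicotine craving among the assessments to be made if a session ends early, without a baseline time. The items of the sensation questionnaire are not in the text: "Stimulation experience scale attached in Notes & Attachments and is the same scale used in all four stages of the protocol".

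**The concern.** Subjects in the second part of Phase 3 abstain for only several hours before the session (section 6.0), so starting craving can differ between them. With no adjustment, that variation stays in the error term of the arm comparison.

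Precision is the point of this part. Section 6.0 gives no power calculation and justifies 15 per group as enough to estimate effect sizes for a later grant application. A rating that is not taken before the session cannot be recovered afterwards.

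**Working it through.** **Is there a baseline to use?** The interval of ten minutes does not exclude a rating at minute 0. But no text names one, and section 6.0 as written would average it into the outcome. With six later ratings (10 to 60 minutes) and a constant effect over them, the raw difference would then be multiplied by 6/7, a loss of 1/7 or 14%. EMA craving is collected between and after sessions, so it gives no value before the first one.

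**Inputs**
- From section 6.0: three groups of 15, and 3 × 15 = 45 agrees with the stated total. There is no power figure to reproduce.
- From the opening of 3.0 Design: d = 0.71, the only effect size in the documents. It refers to tDCS and cigarette consumption, so it serves only as an illustration.
- Assumed: two-sided 0.05 per comparison, random assignment, and r = 0, 0.3, 0.5 or 0.7.

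**Unadjusted, 15 against 15.** The noncentral t has 28 df and noncentrality d·√(15/2). Detectable d at 80% power is 1.06. Power at d = 0.71 is 47%. The 95% CI half-width is 2.048 × √(2/15) = 0.75 SD.

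**Adjusted, two-arm ANCOVA, 27 df.** The variance of the difference is multiplied by (1 − r²)(1 + 1/26). The second term is the average cost of chance baseline imbalance.

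| r | Variance factor | Detectable d, 80% power | Power at d = 0.71 | 95% CI half-width (SD) |
|---|---|---|---|---|
| no covariate | 1 | 1.06 | 47% | 0.75 |
| 0 | 1.04 | 1.08 | 45% | 0.76 |
| 0.3 | 0.95 | 1.03 | 49% | 0.73 |
| 0.5 | 0.78 | 0.94 | 57% | 0.66 |
| 0.7 | 0.53 | 0.77 | 73% | 0.55 |

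A simulation with 40,000 trials per value of r gave power at d = 0.71 of 45%, 49%, 57% and 73%, and type I error of 0.049 to 0.050.

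**One model with all three arms.** Unadjusted (42 df), detectable d is 1.05. With the covariate (41 df, factor (1 − r²)(1 + 1/40)) it is 1.06, 1.01, 0.92 and 0.76 for r = 0, 0.3, 0.5 and 0.7.

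**Break-even.** Adjustment lowers the variance when (1 − r²)(1 + 1/m) < 1, that is r > √(1/(m + 1)).
- 15 per group, two arms, m = 26: r > 0.19
- 15 per group, three arms, m = 40: r > 0.16
- 5 per group, three arms, m = 10: r > 0.30

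At 5 per group the factors for r = 0.3, 0.5 and 0.7 are 1.00, 0.83 and 0.56.

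**Stress test.** An illustrative satiation model assumed starting craving 7 (SD 2), rating SD 1, a one-point effect and strong between-subject variation (drift SD 2, satiation log-SD 0.5). Power rose only from 0.13 to 0.17 with a 50% fall in craving over the session, and from 0.11 to 0.12 with an 80% fall.

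**The case against.** The strongest reply is that an averaged outcome with pairwise tests is a legitimate choice for a pilot meant to estimate effect sizes, and that the benefit rests on an r that nobody has measured. Both statements are true. At r = 0.3 the CI half-width falls by less than 3%, and with strong drift or variable satiation the gain is small. What stands against them is the imbalance of the trade: about 4% more variance at r = 0, against about 47% less at r = 0.7, for one question.

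A second reply is that the phase descriptions are not complete schedules. The TI device section names heart rate and blood pressure, which no phase description mentions, so silence about a baseline craving rating is weak evidence. This stands as a caution. A reader might infer that no craving is measured before stimulation at all. The documents show only that none is clearly scheduled. Even if one is taken, no baseline covariate is named.

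A reader might also infer that the unadjusted comparison is biased. The documents do not support that. It is valid under random assignment. The Phase 3 and 4 text does not state how subjects are assigned, but silence does not show that assignment is non-random.

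A third reply is that the NDSS is already collected before stimulation. It could be considered as a covariate without new data, but it measures dependence, not current craving.

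**Conclusion.** The point holds as an inexpensive improvement, not as an error, and mainly for the second part of Phase 3. The planned comparison leaves starting craving in the error term, and the text provides no clear baseline rating with which to remove it. On the assumed range r = 0.3 to 0.7, the improvement runs from negligible to large. The r = 0 case is the downside.

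Two extensions are tempting but unsupported. The first is that the covariate would make the 5-per-group site choice reliable; at r = 0.3 it gains nothing there. The second is that the same figures apply to Phase 4. They are for a single session, and the documents do not say how the five daily sessions are combined. The later grant's SD is also not a new benefit, since the planned session means already supply it. Only the baseline correlation would be new.

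**What to change.** In 3.0 Design (Phase 3) and section 6.0:
- Schedule one craving rating immediately before stimulation and e-cigarette access, using the same item and range as the in-session ratings. First reconcile the 1-10 range in the Phase 3 design text with the 0-10 range in New technology and section 6.0.
- State that this rating is excluded from the session mean, which uses the ratings at 10 to 60 minutes.
- Prespecify one three-arm ANCOVA with this rating as covariate. Report adjusted differences with 95% CIs and the baseline correlation.
- Do not adjust for in-session nicotine intake, which arises after allocation.
- At 5 per group, show adjusted and unadjusted differences side by side.
- State how subjects are assigned to groups in Phases 3 and 4.

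In Phase 4 the same covariate may be used, but only from the day-1 pre-stimulation rating, because ratings before later sessions follow allocation and stimulation.

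The cost is one extra question and one degree of freedom. If r is below about 0.2 at 15 per group, or about 0.3 at 5 per group, precision falls slightly. The covariate does not remove the effect of nicotine intake on craving during the session.
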